#### **Serious Adverse Event**

A serious adverse event based on ICH and EU Guidelines on Pharmacovigilance for Medicinal Products for Human Use is any untoward medical occurrence that at any dose:

- Results in death
- Is life-threatening  
(The participant was at risk of death at the time of the event. It does not refer to an event that hypothetically might have caused death if it were more severe).
- Requires inpatient hospitalization or prolongation of existing hospitalization
- Results in persistent or significant disability/incapacity
- Is a congenital anomaly/birth defect
- Is a suspected transmission of any infectious agent via a medicinal product
- Is Medically Important\*

\*Medical and scientific judgment should be exercised in deciding whether expedited reporting is also appropriate in other situations, such as important medical events that may not be immediately life threatening or result in death or hospitalization but may jeopardize the participant or may require intervention to prevent one of the other outcomes listed in the definition above. These should usually be considered serious.

## **Unlisted (Unexpected) Adverse Event/Reference Safety Information**

An adverse event is considered unlisted if the nature or severity is not consistent with the applicable product reference safety information. For bermekimab, the expectedness of an adverse event will be determined by whether or not it is listed in the IB.

### **10.5.2. Attribution Definitions**

#### **Assessment of Causality**

The causal relationship to study intervention is determined by the Investigator. The following selection should be used to assess all AEs.

#### **Related**

There is a reasonable causal relationship between study intervention administration and the AE.

#### **Not Related**

There is not a reasonable causal relationship between study intervention administration and the AE.

The term "reasonable causal relationship" means there is evidence to support a causal relationship.

### **10.5.3. Severity Criteria**

An assessment of severity grade will be made using the following general categorical descriptors:

**Mild:** Awareness of symptoms that are easily tolerated, causing minimal discomfort and not interfering with everyday activities.

**Moderate:** Sufficient discomfort is present to cause interference with normal activity.

**Severe:** Extreme distress, causing significant impairment of functioning or incapacitation. Prevents normal everyday activities.

The investigator should use clinical judgment in assessing the severity of events not directly experienced by the participant (eg, laboratory abnormalities).

### **10.5.4. Special Reporting Situations**

Safety events of interest on a sponsor study intervention in an interventional study that may require expedited reporting or safety evaluation include, but are not limited to:

- Overdose of a sponsor study intervention
- Suspected abuse/misuse of a sponsor study intervention
- Accidental or occupational exposure to a sponsor study intervention
- Medication error, intercepted medication error, or potential medication error involving a Johnson & Johnson medicinal product (with or without patient exposure to the Johnson &

Johnson medicinal product, eg, product name confusion, product label confusion, intercepted prescribing or dispensing errors)

- Exposure to a sponsor study intervention from breastfeeding

Special reporting situations should be recorded in the CRF. Any special reporting situation that meets the criteria of a serious adverse event should be recorded on the serious adverse event page of the CRF.

### **10.5.5. Procedures**

#### **All Adverse Events**

All adverse events, regardless of seriousness, severity, or presumed relationship to study intervention, must be recorded using medical terminology in the source document and the CRF. Whenever possible, diagnoses should be given when signs and symptoms are due to a common etiology (eg, cough, runny nose, sneezing, sore throat, and head congestion should be reported as "upper respiratory infection"). Investigators must record in the CRF their opinion concerning the relationship of the adverse event to study therapy. All measures required for adverse event management must be recorded in the source document and reported according to sponsor instructions.

For all studies with an outpatient phase, including open-label studies, the participant must be provided with a "wallet (study) card" and instructed to carry this card with them for the duration of the study indicating the following:

- Study number
- Statement, in the local language(s), that the participant is participating in a clinical study
- Investigator's name and 24-hour contact telephone number
- Local sponsor's name and 24-hour contact telephone number (for medical personnel only)
- Site number
- Participant number
- Any other information that is required to do an emergency breaking of the blind

#### **Serious Adverse Events**

All serious adverse events that have not resolved by the end of the study, or that have not resolved upon the participant's discontinuation from the study, must be followed until any of the following occurs:

- The event resolves
- The event stabilizes
- The event returns to baseline, if a baseline value/status is available
- The event can be attributed to agents other than the study intervention or to factors unrelated to study conduct

- It becomes unlikely that any additional information can be obtained (participant or health care practitioner refusal to provide additional information, lost to follow-up after demonstration of due diligence with follow-up efforts)

Suspected transmission of an infectious agent by a medicinal product will be reported as a serious adverse event.

Any event requiring hospitalization (or prolongation of hospitalization) that occurs during the course of a participant's participation in a study must be reported as a serious adverse event, except hospitalizations for the following:

- Hospitalizations not intended to treat an acute illness or adverse event (eg, social reasons such as pending placement in long-term care facility)
- Surgery or procedure planned before entry into the study (must be documented in the CRF). Note: Hospitalizations that were planned before the signing of the ICF, and where the underlying condition for which the hospitalization was planned has not worsened, will not be considered serious adverse events. Any adverse event that results in a prolongation of the originally planned hospitalization is to be reported as a new serious adverse event.

The cause of death of a participant in a study within 4 weeks of the last administration of study intervention, whether or not the event is expected or associated with the study intervention, is considered a serious adverse event.

Information regarding serious adverse events will be transmitted to the sponsor using a serious adverse event reporting form and safety report form of the CRF, which must be completed and reviewed by a physician from the study site and transmitted in a secure manner to the sponsor within 24 hours. The initial and follow-up reports of a serious adverse event should be transmitted in a secure manner electronically or by facsimile (fax). Telephone reporting should be the exception and the reporter should be asked to complete the appropriate form(s) first.

#### **10.5.6. Product Quality Complaint Handling**

##### **Definition**

A PQC is defined as any suspicion of a product defect related to manufacturing, labeling, or packaging, ie, any dissatisfaction relative to the identity, quality, durability, reliability, or performance of a distributed product, including its labeling, drug delivery system, or package integrity. A PQC may have an impact on the safety and efficacy of the product. In addition, it includes any technical complaints, defined as any complaint that indicates a potential quality issue during manufacturing, packaging, release testing, stability monitoring, dose preparation, storage or distribution of the product or the drug delivery system.

Timely, accurate, and complete reporting and analysis of PQC information from studies are crucial for the protection of participants, investigators, and the sponsor, and are mandated by regulatory agencies worldwide. The sponsor has established procedures in conformity with regulatory

requirements worldwide to ensure appropriate reporting of PQC information; all studies conducted by the sponsor or its affiliates will be conducted in accordance with those procedures.

### **Procedures**

All initial PQCs must be reported to the sponsor by the study-site personnel within 24 hours after being made aware of the event.

A sample of the suspected product should be maintained under the correct storage conditions until a shipment request is received from the sponsor.

#### **10.5.7. Contacting Sponsor Regarding Safety, Including Product Quality**

The names (and corresponding telephone numbers) of the individuals who should be contacted regarding safety issues, PQC, or questions regarding the study are listed in the Contact Information page(s), which will be provided as a separate document.

## 10.6. Appendix 6: Contraceptive Guidance

Participants must follow contraceptive measures as outlined in Section 5.1, Inclusion Criteria. Pregnancy information will be collected and reported as noted in Section 8.3.5, Pregnancy and Appendix 3 Adverse Events, Serious Adverse Events, Product Quality Complaints, and Other Safety Reporting: Definitions and Procedures for Recording, Evaluating, Follow-up, and Reporting.

### Definitions

#### *Woman of Childbearing Potential (WOCBP)*

A woman is considered fertile following menarche and until becoming postmenopausal unless permanently sterile (see below).

#### *Woman Not of Childbearing Potential*

- **premenarchal**  
A premenarchal state is one in which menarche has not yet occurred.
- **postmenopausal**  
A postmenopausal state is defined as no menses for 12 months without an alternative medical cause. A high follicle stimulating hormone (FSH) level (>40 IU/L or mIU/mL) in the postmenopausal range may be used to confirm a postmenopausal state in women not using hormonal contraception or hormonal replacement therapy (HRT), however in the absence of 12 months of amenorrhea, a single FSH measurement is insufficient. If there is a question about menopausal status in women on HRT, the woman will be required to use one of the non-estrogen-containing hormonal highly effective contraceptive methods if she wishes to continue HRT during the study.
- **permanently sterile (for the purpose of this study)**  
Permanent sterilization methods include hysterectomy, bilateral salpingectomy, and bilateral oophorectomy.

Note: If the childbearing potential changes after start of the study (eg, a premenarchal woman experiences menarche) or the risk of pregnancy changes (eg, a woman who is not heterosexually active becomes active), a woman must begin a highly effective method of contraception, as described throughout the inclusion criteria.

If reproductive status is questionable, additional evaluation should be considered.

Contraceptive (birth control) use by men or women should be consistent with local regulations regarding the acceptable methods of contraception for those participating in clinical studies.

Typical use failure rates may differ from those when used consistently and correctly. Use should be consistent with local regulations regarding the use of contraceptive methods for participants in clinical studies.

## Examples of Contraceptives

EXAMPLES OF CONTRACEPTIVESa ALLOWED FOR FEMALE PARTICIPANTS DURING THE STUDY INCLUDE:
USER INDEPENDENT
Highly Effective Methods That Are User Independent Failure rate of <1% per year when used consistently and correctly.

 
• Implantable progestogen-only hormone contraception associated with inhibition of ovulationb
 

 
• Intrauterine device (IUD)
 

 
• Intrauterine hormone-releasing system (IUS)
 

 
• Tubal closure (eg, bilateral tubal occlusion, bilateral tubal ligation)
 

 
• Azoospermic partner (vasectomized or due to medical cause) (Vasectomized partner is a highly effective contraceptive method provided that the partner is the sole sexual partner of the woman of childbearing potential and the absence of sperm has been confirmed. If not, additional highly effective method of contraception should be used. Spermatogenesis cycle is approximately 74 days.)
 

USER DEPENDENT
Highly Effective Methods That Are User Dependent Failure rate of <1% per year when used consistently and correctly.

 
• Combined (estrogen- and progestogen-containing) hormonal contraception associated with inhibition of ovulationb 
 
– oral
 
– intravaginal
 
– transdermal
 
– injectable
 
 
 

 
• Progestogen-only hormone contraception associated with inhibition of ovulationb 
 
– oral
 
– injectable
 
 
 

 
• Sexual abstinence (Sexual abstinence is considered a highly effective method only if defined as refraining from heterosexual intercourse during the entire period of risk associated with the study intervention. The reliability of sexual abstinence needs to be evaluated in relation to the duration of the study and the preferred and usual lifestyle of the participant.)
 

NOT ALLOWED AS SOLE METHOD OF CONTRACEPTION DURING THE STUDY (not considered to be highly effective- failure rate of ≥1% per year)

 
• Progestogen-only oral hormonal contraception where inhibition of ovulation is not the primary mode of action.
 

 
• Female condom with or without spermicidec
 

 
• Cap, diaphragm, or sponge with spermicide
 

 
• Periodic abstinence (calendar, symptothermal, post-ovulation methods)
 

 
• Withdrawal (coitus-interruptus)
 

 
• Spermicides alone
 

 
• Lactational amenorrhea method (LAM)
 

- a) Typical use failure rates may differ from those when used consistently and correctly. Use should be consistent with local regulations regarding the use of contraceptive methods for participants in clinical studies.
- b) Hormonal contraception may be susceptible to interaction with the study intervention, which may reduce the efficacy of the contraceptive method. In addition, consider if the hormonal contraception may interact with the study intervention.
- c) Male condom and female condom should not be used together (due to risk of failure with friction).

### **Pregnancy During the Study**

All initial reports of pregnancy in female participants or partners of male participants must be reported to the sponsor or designee by the study-site personnel within 24 hours of their knowledge of the event using the appropriate pregnancy notification form. Abnormal pregnancy outcomes (eg, spontaneous abortion, fetal death, stillbirth, congenital anomalies, ectopic pregnancy) are considered SAEs and must be reported using the Serious Adverse Event Form. Any participant who becomes pregnant during the study must discontinue further study intervention. Follow-up information regarding the outcome of the pregnancy and any postnatal sequelae in the infant will be required.

### 10.7. Appendix 7: Hepatitis B Virus (HBV) Screening with HBV DNA Testing

Participants must undergo screening for hepatitis B virus (HBV). At a minimum, this includes testing for HBsAg (HBV surface antigen), anti-HBs (HBV surface antibody), and anti-HBc total (HBV core antibody total):

- Participants who test negative for all HBV screening tests (ie, HBsAg-, anti-HBc-, and anti-HBs-) **are eligible** for this study.
- Participants who test **negative** for surface antigen (HBsAg-) and test **positive** for core antibody (anti-HBc+) **and** surface antibody (anti-HBs+) **are eligible** for this study. If required by local guidelines, only subjects who have undergone HBV DNA testing and confirmed negative will be eligible.
- Participants who test **positive only** for **surface antibody** (anti-HBs+) **are eligible** for this study. If required by local guidelines, only subjects who have undergone HBV DNA testing and confirmed negative will be eligible.
- Participants who test **positive** for surface antigen (HBsAg+) **are NOT eligible** for this study, regardless of the results of other hepatitis B tests.
- Participants who test **positive only** for **core antibody** (anti-HBc+) must undergo further testing for the presence of hepatitis B virus deoxyribonucleic acid (HBV DNA test). If the HBV DNA test is **positive**, the subject **is NOT eligible** for this study. If the HBV DNA test is **negative**, the subject **is eligible** for this study. In the event the HBV DNA test cannot be performed, the subject **is NOT eligible** for this study.

For participants who **are not eligible for this study due to HBV test results**, consultation with a physician with expertise in the treatment of hepatitis B virus infection is recommended. For subjects who are eligible with surface antigen (HBsAg) negative, core antibody (anti-HBc) and/or surface antibody (anti-HBs) positive, and HBV DNA test is negative, HBV DNA quantitation should be monitored according to local guidelines.

For Japan sites only: Participants with surface antigen (HBsAg) negative, core antibody (anti-HBc), and/or surface antibody (anti-HBs) positive test results must undergo further HBV DNA testing. If the HBV DNA test is negative, the participant is eligible for this study and the HBV DNA testing should be performed every 4 weeks.

Eligibility based on hepatitis B virus test results			
Action	Hepatitis B test result		
	Hepatitis B surface antigen (HBsAg)	Hepatitis B surface antibody (anti-HBs)	Hepatitis B core antibody (anti-HBc total)
Include	—	—	—
	—	+**	—
	—	+**	+
Exclude	+	— or +	— or +
Require testing for presence HBV DNA*	—	—	+

* If HBV DNA is detectable, exclude from the clinical study. If HBV DNA testing cannot be performed, or there is evidence of chronic liver disease, exclude from the clinical study.
 
**If required by local guidelines, only subjects who have undergone HBV DNA testing and confirmed negative will be eligible.
			

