### **2.3. Benefit-Risk Assessment**

Based on the available data and the proposed safety measures discussed below, the risks of the dose regimens of bermekimab to be investigated in this protocol appear to be acceptable relative to the potential benefit.

Bermekimab has undergone previous clinical development in diseases such as psoriasis, AD, HS, acne vulgaris, pyoderma gangrenosum and cancer, as summarized in the latest version of the IB. The collective efficacy and safety results of the Phase 1 and Phase 2 clinical studies in healthy volunteers and patients in dermatologic indications have indicated a favorable benefit-risk profile for further bermekimab development to date. In addition, nonclinical evidence that IL-1a may be an important component for inducing chronic skin inflammation ([Abdel-Razzak 1993](#), [Murphy 2000](#)).

Unblinded safety will be evaluated on an ongoing basis throughout this study by an independent Data Monitoring Committee (iDMC), in addition to the standard safety oversight performed by the sponsor.

The risks for bermekimab are infections, hypersensitivity reactions and injection-site reactions. More detailed information about the known and expected benefits and risks of bermekimab may be found in the IB.

The important risks for adalimumab are:

1. serious infections which may be fatal and include opportunistic infections such as tuberculosis (TB) and invasive fungal infection (patients over 65 years of age were found to be at higher risk for infection);
2. malignancies which may be fatal (including lymphoma and hepatosplenic T-cell lymphoma);
3. anaphylaxis or serious allergic reactions;
4. Hepatitis B virus (HBV) reactivation;
5. demyelinating disease;
6. cytopenias and pancytopenia;
7. heart failure;
8. Lupus-like syndrome;
9. Concomitant administration of adalimumab with anakinra (human interleukin-1 receptor antagonist) is not recommended based on the possible increased risk for infections, including serious infections which were observed with anakinra and etanercept (another TNF-blocker) studies ([Humira SmPC 2021](#)). Bermekimab has not been evaluated in clinical studies with TNF blockers.

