## 5.2. Exclusion Criteria

Any potential participant who meets any of the following criteria will be excluded from participating in the study:

1. Has a current diagnosis or signs or symptoms of severe, progressive, or uncontrolled renal, cardiac, vascular, pulmonary, gastrointestinal, endocrine, neurologic, hematologic, rheumatologic, psychiatric, or metabolic disturbances.
2. Has unstable cardiovascular disease, defined as a recent clinical deterioration (eg, unstable angina, rapid atrial fibrillation) in the last 3 months or a cardiac hospitalization within the last 3 months.
3. Has a history of lymphoproliferative disease, including lymphoma; a history of monoclonal gammopathy of undetermined significance; or signs and symptoms suggestive of possible lymphoproliferative disease, such as lymphadenopathy or splenomegaly.
4. A history of malignancy within 5 years before screening (exceptions are squamous and basal cell carcinomas of the skin and carcinoma in situ of the cervix, or malignancy, which is considered cured with no evidence of recurrence for at least 3 months prior to the first administration of study intervention and with minimal risk of recurrence).
5. Has a history of chronic or recurrent infectious disease, including but not limited to chronic renal infection, chronic chest infection (e.g., bronchiectasis), recurrent urinary tract infection (recurrent pyelonephritis or chronic nonremitting cystitis), fungal infection (mucocutaneous candidiasis), or open, draining, or infected skin wounds or ulcers (not related to HS).
6. Has or has had a serious infection (e.g., sepsis, pneumonia, or pyelonephritis), or has been hospitalized or received IV antibiotics for an infection during the 2 months before screening.
7. Has or has had herpes zoster within the 2 months before screening.

8. Has a history of an infected joint prosthesis or has received antibiotics for a suspected infection of a joint prosthesis, if that prosthesis has not been removed or replaced.
9. Is infected with human immunodeficiency virus (HIV), positive serology for HIV antibody).
10. Tests positive for HBV infection (see Section 10.7) or who are seropositive for antibodies to hepatitis C virus (HCV) at screening.

11. Criterion modified per Amendment 1:

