#### Phase 2 Liver Chemistry Stopping Criteria and Increased Monitoring Algorithm (no preexisting liver disease)

#### 10.19.2. Follow up Assessments

#### Phase 2 Liver Chemistry Stopping Criteria and Follow-up Assessments

Phase 2 liver chemistry stopping criteria are designed to assure participant safety and to evaluate liver event etiology. In patients with alternative clinical reasons for elevated liver enzymes (for example, patients experiencing exercise induced CPK elevation or cholelithiasis), rechallenge with investigational product may be possible after discussion with medical monitor.

Liver Chemistry Stopping Criteria	
ALT/AST-absolute	ALT or AST- $\geq 5 \times \text{ULN}$
ALT/AST-Increase	
If cannot monitor: ALT or AST- <math>\geq 3 \times \text{ULN}</math> and cannot be monitored weekly for 4 weeks
 
Or if able to monitor: ALT or AST- <math>\geq 3 \times \text{ULN}</math> persists for <math>\geq 4</math> weeks

Total bilirubin	ALT or AST- $\geq 3 \times \text{ULN}$ and total bilirubin $\geq 2 \times \text{ULN}$ (or at least a doubling of direct bilirubin in known Gilbert's syndrome)
INR^2	ALT or AST- $\geq 3 \times \text{ULN}$ and international normalized ratio (INR) $> 1.5$ , if INR measured
Symptomatic	ALT or AST- $\geq 3 \times \text{ULN}$ associated with symptoms (new or worsening) believed to be related to liver injury or hypersensitivity
Suggested Actions, Monitoring and Follow-up Assessments	
Actions	Follow-up Assessments

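### Appendix 7 text and table give opposite eligibility answers for a core-antibody-only, HBV-DNA-negative participant with evidence of chronic liver disease

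*Protocol*

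**What the plan says.** Exclusion Criterion 10 in protocol Section 5.2 sends the reader to Section 10.7 for hepatitis B eligibility. It does not say whether the text or the table there governs.

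**Text of Section 10.7.** For the group negative for surface antigen and surface antibody but positive for core antibody: "Participants who test positive only for core antibody (anti-HBc+) must undergo further testing" for HBV DNA. Three outcomes follow. A positive test means not eligible. A test that cannot be done means not eligible. For a negative test: "If the HBV DNA test is negative, the subject is eligible for this study". The bullet attaches no liver condition.

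**Japan paragraph of Section 10.7.** Participants negative for surface antigen and positive for core antibody, surface antibody or both must have HBV DNA testing, and "If the HBV DNA test is negative, the participant is eligible for this study", with repeat testing every 4 weeks. Again there is no liver condition.

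**Table in Section 10.7.** The row for the core-antibody-only pattern carries an asterisk. Its footnote excludes participants with detectable HBV DNA and then states: "If HBV DNA testing cannot be performed, or there is evidence of chronic liver disease, exclude from the clinical study".

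**The concern.** The bullet and the footnoted row describe the same serology, and both set out who may enter on hepatitis B results. The liver condition appears only in the footnote. A site working from the bullets could accept a candidate whom a site working from the table would refuse.

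The matter is safety related: Section 2.3 lists "Hepatitis B virus (HBV) reactivation" among the important risks of adalimumab, which is one of three equally allocated arms in Part 1. It also bears on how deviations are classified. Section 5 allows no waivers, and Appendix 4 of the SAP lists entry without satisfying the criteria as a category of major protocol deviation. Whether such a participant counts under that category depends on which half of Appendix 7 is applied.

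**Working it through.** No arithmetic applies. The check compares the two statements of the rule for the core-antibody-only group, outcome by outcome, and then looks for any other criterion that would settle a difference.

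| Case | Section 10.7 bullet | Section 10.7 table and footnote | Agree? |
|---|---|---|---|
| HBV DNA positive | Not eligible | Exclude | Yes |
| HBV DNA test not possible | Not eligible | Exclude | Yes |
| HBV DNA negative, no chronic liver disease | Eligible | No ground to exclude | Yes |
| HBV DNA negative, evidence of chronic liver disease | Eligible | Exclude | **No** |

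The conflict is confined to the fourth case. A core-antibody-only participant in Japan meets it too, because the Japan paragraph makes a negative DNA test sufficient. That paragraph also covers surface-antibody-positive patterns, whose table rows do not carry the asterisk.

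The other criteria were then checked for a rule that resolves the fourth case:

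- **Exclusion Criterion 10** only points back to Section 10.7.
- **Exclusion Criterion 1** covers conditions that are "severe, progressive, or uncontrolled renal, cardiac, vascular, pulmonary, gastrointestinal, endocrine" and several further systems, but it does not name the liver. Even if one of the listed systems were read to include it, the disease must be severe, progressive or uncontrolled.
- **Inclusion Criterion 2** asks for general good health, with any abnormality consistent with the study disease. It would stop some of these candidates, but by the investigator's determination.
- **Inclusion Criterion 7.1** requires suitability for adalimumab under local labelling. It applies to Part 1 only and rests on the investigator's opinion.
- **Inclusion Criterion 10, items f to h**, limits AST, ALT and alkaline phosphatase to twice the upper limit of normal. These are enzyme limits; they do not exclude chronic liver disease with values inside them.
- **Exclusion Criterion 41** is a general judgement about the participant's interest or interference with assessments.

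None of these names chronic liver disease, and nothing in Section 10.7 or Section 5.2 says whether text or table takes precedence.

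**The case against.** The best defence is that the two passages are cumulative. Exclusion Criterion 10 refers to Section 10.7 as a whole, and the table is part of it. Eligible in a bullet cannot mean eligible without regard to anything else, since all other criteria still apply. On that reading the bullet gives the consequence of a test result and the footnote adds a condition. A careful site could well read it so. What weakens the defence is that the bullet lists what look like all the outcomes for that serology, two of the footnote's three exclusions are repeated there, and the third is missing without a cross-reference.

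A second defence is that Section 5 requires the investigator to resolve any question about the criteria with the sponsor before enrolling. That stands for a site that notices the conflict. A site that reads only the bullet sees no question to raise.

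A third is that the general criteria listed above leave little practical room for such an enrolment. This stands in part and is the main reason for treating the point as minor.

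Two stronger readings are tempting, and the documents do not support them:

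- A reader might infer that the HBV DNA monitoring sentence contradicts the testing rule. It covers eligible participants who are "core antibody (anti-HBc) and/or surface antibody (anti-HBs) positive, and HBV DNA test is negative, HBV DNA quantitation should be monitored", while participants positive for both antibodies outside Japan may enter without a DNA test. But that testing is required where local guidelines ask for it, and the monitoring is also to follow local guidelines. Both defer to the same standard, so they do not contradict each other.
- A reader might infer that a participant admitted under the bullet falls outside the liver stopping rules, because a title in Appendix 19 reads "Increased Monitoring Algorithm (no preexisting liver disease". That title stands before the heading of Section 10.19.2 and so belongs to Section 10.19.1, whose discontinuation statement applies to any participant meeting the stopping criteria. Section 10.19.2 has its own title without that restriction.

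**Conclusion.** The inconsistency is real but narrow. It concerns one combination: positive only for core antibody, HBV DNA negative, evidence of chronic liver disease, and passing every other criterion. For that person the Appendix 7 bullet and the Japan paragraph say eligible, and the table footnote says exclude.

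The documents give no prevalence for this combination. That few candidates are affected is therefore an assumption, resting on how many conditions must coincide. No endpoint, power figure or analysis changes. The documents do not support the inference that such participants would in fact be enrolled: eligible here means eligible under Appendix 7 only, and other criteria could still refuse them.

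Severity is minor. SAP Section 1 records the decision of 14 October 2022 to terminate the study, so what remains is consistent classification of eligibility deviations and not carrying the wording into another protocol. Which rule is right is not a question this comparison can answer.

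**What to change.** Reconcile three places in Section 10.7 so that they state the same rule in the same words: the core-antibody-only bullet, the Japan paragraph and the asterisk footnote. The sponsor should decide the rule and state which serology rows it covers. No change to the HBV DNA monitoring sentence or to the titles in Appendix 19 is needed for this point.

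The cost is a few words in one appendix. No sample size, analysis or schedule is affected.
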